6.3. Prohibited Concomitant Medications and Products

6.3.1. Prohibited Concomitant Medications and Products for Ibrutinib and/or Venetoclax

Any non-study protocol related chemotherapy, anti-cancer immunotherapy, experimental therapy, or radiotherapy for the underlying B-cell malignancy are prohibited while the subject is receiving ibrutinib treatment.

Corticosteroids for the treatment of the underlying malignancy are prohibited (Refer to [Section 6.1](#) for further guidance).

The Sponsor must be notified in advance (or as soon as possible thereafter) of any instances in which prohibited therapies are administered.

Use of strong CYP3A inhibitors is contraindicated during venetoclax initiation and dose ramp-up. Subjects may not consume grapefruit or grapefruit products, Seville oranges (including marmalade containing Seville oranges) or starfruit within the 3-day period prior to the first venetoclax administration and until the last day of treatment is completed due to possible CYP3A mediated metabolic interaction.

6.4. Guidelines for Ibrutinib Management with Surgeries or Procedures

Ibrutinib may increase risk of bleeding with invasive procedures or surgery. The following guidance should be applied to the use of ibrutinib in the perioperative period for subjects who require surgical intervention or an invasive procedure while receiving ibrutinib:

6.4.1. Minor Surgical Procedures

For minor procedures (such as a central line placement, needle biopsy, lumbar puncture [other than shunt reservoir access], thoracentesis, or paracentesis) ibrutinib should be held for at least 3 days prior to the procedure and should not be restarted for at least 3 days after the procedure. For bone marrow biopsies that are performed while the subject is on ibrutinib, it is not necessary to hold ibrutinib.

6.4.2. Major Surgical Procedures

For any surgery or invasive procedure requiring sutures or staples for closure, ibrutinib should be held at least 7 days prior to the intervention and should be held at least 7 days after the procedure and restarted at the discretion of the investigator when the surgical site is reasonably healed without serosanguineous drainage or the need for drainage tubes.

6.4.3. Emergency Procedures

For emergency procedures, ibrutinib should be held as soon as possible and until the surgical site is reasonably healed or for at least 7 days after the urgent surgical procedure, whichever is longer.

7. STUDY EVALUATIONS

7.1. Description of Procedures

7.1.1. Assessments

7.1.1.1. ICF

The subject must read, understand, and sign the Institutional Review Board/Research Ethics Board/Independent Ethics Committee (IRB/REB/IEC) approved ICF confirming his or her willingness to participate in this study before any study-specific screening procedures are performed. Subjects must also grant permission to use protected health information per the Health Insurance Portability and Accountability Act (HIPAA). In addition, subjects must sign all approved ICF amendments per the site IRB/REB/IEC guidelines during the course of the study.

7.1.1.2. Confirm Eligibility

All necessary procedures and evaluations must be performed to document that the subject meets all of the inclusion criteria and none of the exclusion criteria prior to first dose on Day 1 ([Section 4](#)).

7.1.1.3. Medical History and Demographics

The subject's relevant medical history through review of medical records and by interview will be collected and recorded. The medical history collection period is defined as disease history up until first dose. Concurrent medical signs and symptoms must be documented to establish baseline severities. A disease history, including the date of initial diagnosis, Rai staging ([Appendix M](#)) within 28 days of first dose with study drug will be recorded.

7.1.1.4. Prior and Concomitant Medications

All active medications from the signing of ICF or at least 14 days prior to first dose through 30 days after the last dose of study drug will be documented.

7.1.1.5. Adverse Events

The accepted regulatory definition for an adverse event (AE) is provided in [Section 11.1](#). The occurrence of AE from the time the ICF is signed until first dose should be recorded under medical history in the eCRF form. All medical occurrences after the first dose with study drug until 30 days after the last dose of study drug that meet the AE definition must be recorded as AEs in the eCRF. Laboratory abnormalities designated clinically significant by the investigator will also be documented as AEs. Additional important requirements for AE and SAE reporting are explained in [Section 11.4](#).

7.1.1.6. Physical Examination

The Screening and End-of-Treatment physical examination will include, at a minimum, the general appearance of the subject, height (screening only) and weight, and examination of the skin, eyes, ears, nose, throat, lungs, heart, abdomen, extremities, musculoskeletal system, nervous system, and lymphatic system.

7.1.1.7. ECOG

The ECOG performance status is provided in [Appendix F](#). Performance status will only be collected until disease progression.

7.1.1.8. Vital Signs

Vital signs will include blood pressure, heart rate, and body temperature after the subject has rested in a sitting position for at least 3 minutes.

7.1.1.9. Tumor Lysis Syndrome (TLS) Risk Assessment

At baseline and prior to initiating venetoclax in Cycle 4, all study subjects will be assessed for risk of developing TLS. Ongoing risk of TLS should be assessed at all ramp up visits. The risk of TLS is a continuum based on multiple factors, including comorbidities. Subjects with high tumor burden (eg, any lymph node with a diameter ≥ 5 cm or high absolute lymphocyte count (ALC) [ALC $\geq 25 \times 10^9/L$]) are at greater risk of TLS when initiating venetoclax. Reduced renal function (creatinine clearance [CrCl] < 80 mL/min) further increases the risk. The risk may decrease as tumor burden decreases with venetoclax treatment.

Tumor burden assessments, including radiographic evaluation (eg, CT scans) as well as blood chemistry (creatinine, uric acid, potassium, phosphorus, and calcium) assessments will be performed in all subjects prior to initiating venetoclax treatment.

Appropriate venetoclax dosing and management of subjects throughout their study treatment is guided by their individual risk for developing TLS. Risk-based TLS prophylaxis and management measures are described in [Section 5.4.2.2](#).

7.1.1.10. Tumor Lysis Syndrome (TLS) Prophylaxis

For subjects at risk of TLS per investigator assessment, the prophylaxis measures listed in [Section 5.4.2.2](#) should be followed and more intensive measures (including hospitalization) should be employed as overall risk increases. These measures should be performed prior to initiating therapy with venetoclax (2-3 days prior to first dose) and throughout the ramp-up phase, especially the first day of each ramp-up dose. Refer to Schedule of Assessments ([Appendix A](#), [Appendix B](#), [Appendix D](#), and [Appendix E](#)) for specific timepoints of assessments.

7.1.2. Laboratory

7.1.2.1. Hematology

Hematology parameters will include a complete blood count: white blood cells, red blood cells, hemoglobin, hematocrit, platelets, neutrophils, bands, lymphocytes, prolymphocytes, atypical lymphocytes (if found on routine CBC review), monocytes, eosinophils, and basophils.

Hematology samples will be collected and tested by local laboratory.

7.1.2.2. Chemistry (Serum)

Serum chemistry parameters will include: sodium, potassium, chloride, blood urea nitrogen (BUN)/Urea, creatinine, glucose, calcium, total protein, albumin, AST, ALT, alkaline phosphatase, total bilirubin, LDH, phosphate/inorganic phosphorus, uric acid, magnesium, and bicarbonate. Chemistry samples will be collected and tested by local laboratory.

7.1.2.3. Coagulation Studies

Measurement of PT/INR and aPTT will be performed at Screening and Reintroduction using a local laboratory.

7.1.2.4. Hepatitis Serologies

Hepatitis serologies include hepatitis C antibody, hepatitis B surface antibody, hepatitis B core antibody, and hepatitis B surface antigen (HBsAg). If hepatitis B core antibody, hepatitis B surface antigen, or hepatitis C antibody is positive, then PCR to quantitate hepatitis B DNA or hepatitis C RNA must be performed and must be negative prior to enrollment. Subjects who are HBsAg positive are excluded. Hepatitis serologies will be collected and tested by local laboratory.

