	
8. Recent infection requiring systemic treatment that is ongoing or was completed ≤ 14 days before the first dose of study drug, or any uncontrolled active systemic infection.9. Known bleeding disorders (eg, von Willebrand's disease or hemophilia).10. History of stroke or intracranial hemorrhage within 6 months prior to enrollment.11. Known history of human immunodeficiency virus (HIV) or active infection with hepatitis C virus (HCV) or hepatitis B virus (HBV). Subjects who are positive for hepatitis B core antibody, hepatitis B surface antigen (HBs Ag), or hepatitis C antibody must have a negative polymerase chain reaction (PCR) result before enrollment. Those who are PCR positive will be excluded.12. Major surgery within 4 weeks of first dose of study drug.13. Any life-threatening illness, medical condition, or organ system dysfunction that, in the investigator's opinion, could compromise the subject's safety or put the study outcomes at undue risk.14. Currently active, clinically significant cardiovascular disease, such as uncontrolled arrhythmia or Class 3 or 4 congestive heart failure as defined by the New York Heart Association Functional Classification; or a history of myocardial infarction, unstable angina, or acute coronary syndrome within 6 months prior to enrollment.15. Unable to swallow capsules/tablets or malabsorption syndrome, disease significantly affecting gastrointestinal function, or resection of the stomach or small bowel, symptomatic inflammatory bowel disease or ulcerative colitis, or partial or complete bowel obstruction.16. Concomitant use of warfarin or other vitamin K antagonists.17. Requires treatment with a strong cytochrome P450 (CYP) 3A inhibitor (see Appendix G).18. Currently active, clinically significant hepatic impairment Child-Pugh Class B or C according to the Child Pugh classification (see Appendix K).19. Lactating or pregnant.20. Unwilling or unable to participate in all required study evaluations and procedures.21. Unable to understand the purpose and risks of the study and to provide a signed and dated informed consent form (ICF) and authorization to use protected health information (in accordance with national and local subject privacy regulations).22. Uncontrolled autoimmune hemolytic anemia or idiopathic thrombocytopenia purpura, such as those subjects with a declining hemoglobin level or platelet count secondary to autoimmune destruction within the 4 weeks prior to first dose of study drug, or the need for daily prednisone >20 mg daily (or corticosteroid equivalent) to treat or control the autoimmune disease.

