4.2. Exclusion Criteria

To be enrolled in the study, potential subjects must meet NONE of the following exclusion criteria:

1. Any prior therapy (including but not limited to chemotherapy, targeted therapy, immunomodulating therapy, radiotherapy, and/or monoclonal antibody) used for treatment of CLL or SLL.
2. History of other malignancies, except:
 - Malignancy treated with curative intent and with no known active disease present for ≥ 3 years before the first dose of study drug and felt to be at low risk for recurrence by the treating physician
 - Adequately treated non-melanoma skin cancer or lentigo maligna without evidence of disease
 - Adequately treated carcinoma in situ without evidence of disease
3. Known or suspected history of Richter's transformation.
4. Concurrent administration of >20 mg/day of prednisone within 7 days of initiation of study drug unless indicated for prophylaxis or management of allergic reactions (eg, contrast).
5. Known hypersensitivity to one or more study drugs.
6. Known allergy to xanthine oxidase inhibitors and/or rasburicase. Subjects who are allergic to xanthine oxidase inhibitors and cannot receive rasburicase will be excluded.
7. Vaccinated with live, attenuated vaccines within 4 weeks of first dose of study drug.
8. Recent infection requiring systemic treatment that is ongoing or was completed ≤ 14 days before the first dose of study drug, or any uncontrolled active systemic infection.

² Complete abstinence is a highly effective method only if defined as refraining from heterosexual intercourse during the entire period of risk associated with the study treatments. The reliability of sexual abstinence needs to be evaluated in relation to the duration of the clinical trial and the preferred and usual lifestyle of the subject.

http://www.hma.eu/fileadmin/dateien/Human_Medicines/01

About_HMA/Working_Groups/CTFG/2014_09_HMA_CTFG_Contraception.pdf

9. Known bleeding disorders (eg, von Willebrand's disease or hemophilia).
10. History of stroke or intracranial hemorrhage within 6 months prior to enrollment.
11. Known history of human immunodeficiency virus (HIV) or active infection with hepatitis C virus (HCV) or hepatitis B virus (HBV). Subjects who are positive for hepatitis B core antibody, hepatitis B surface antigen (HBsAg), or hepatitis C antibody must have a negative polymerase chain reaction (PCR) result before enrollment. Those who are PCR positive will be excluded.

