12. Major surgery within 4 weeks of first dose of study drug.
13. Any life-threatening illness, medical condition, or organ system dysfunction that, in the investigator's opinion, could compromise the subject's safety or put the study outcomes at undue risk.
14. Currently active, clinically significant cardiovascular disease, such as uncontrolled arrhythmia or Class 3 or 4 congestive heart failure as defined by the New York Heart Association Functional Classification; or a history of myocardial infarction, unstable angina, or acute coronary syndrome within 6 months prior to enrollment.
15. Unable to swallow capsules/tablets or malabsorption syndrome, disease significantly affecting gastrointestinal function, or resection of the stomach or small bowel, symptomatic inflammatory bowel disease or ulcerative colitis, or partial or complete bowel obstruction.
16. Concomitant use of warfarin or other vitamin K antagonists.
17. Requires treatment with a strong cytochrome P450 (CYP) 3A inhibitor (see [Appendix G](#)).
18. Currently active, clinically significant hepatic impairment Child-Pugh Class B or C according to the Child Pugh classification ([Appendix K](#)).
19. Lactating or pregnant.
20. Unwilling or unable to participate in all required study evaluations and procedures.
21. Unable to understand the purpose and risks of the study and to provide a signed and dated informed consent form (ICF) and authorization to use protected health information (in accordance with national and local subject privacy regulations).
22. Uncontrolled autoimmune hemolytic anemia or idiopathic thrombocytopenia purpura, such as those subjects with a declining hemoglobin level or platelet count secondary to autoimmune destruction within the 4 weeks prior to first dose of study drug, or the need for daily prednisone >20 mg daily (or corticosteroid equivalent) to treat or control the autoimmune disease.

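### Exclusion criterion 11 omits the HBsAg exclusion stated in Protocol 7.1.2.4 and implies that a negative PCR clears an HBsAg-positive subject

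*Protocol*

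**What the plan says.** Criterion 11 appears twice. The synopsis names the core antibody as the first marker, and its list then goes on as follows: "hepatitis B surface antigen (HBs Ag), or hepatitis C antibody must have a negative polymerase chain reaction (PCR) result before enrollment". Section 4.2 has the same rule: "hepatitis B surface antigen (HBsAg), or hepatitis C antibody must have a negative polymerase chain reaction (PCR) result before enrollment". Both versions then say who is barred on serology: "Those who are PCR positive will be excluded". The opening sentence of the criterion separately excludes known HIV and active viral hepatitis ("active infection with hepatitis C virus (HCV) or hepatitis B virus (HBV").

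Protocol 7.1.2.4 (Hepatitis Serologies) begins with the same route: "If hepatitis B core antibody, hepatitis B surface antigen, or hepatitis C antibody is positive, then PCR" must be done and must be negative before enrolment. Its next sentence is "Subjects who are HBsAg positive are excluded".

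Protocol 7.1.1.2 sets the standard for eligibility. The site must document that the subject "meets all of the inclusion criteria and none of the exclusion criteria prior to first dose on Day 1", with a reference to Section 4. The Cycle 1 Day 1 visit lists in 8.2.1.1 and 8.3.1.1 also confirm eligibility against the inclusion and exclusion criteria. Footnote k in Appendices A and B, attached to the hepatitis serology row, refers to 7.1.2.4.

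**The concern.** A rule that bars subjects belongs in the exclusion list, because that is the list sites check. Here the strict rule appears only in a description of laboratory procedures. The exclusion list treats HBsAg in the same way as core antibody and hepatitis C antibody, as a marker followed up by PCR. A site working from criterion 11 alone could take a negative PCR as clearance and enrol a subject whom 7.1.2.4 bars. Different sites could decide the same case differently.

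The stake is safety. Protocol 1.2.4.5 reports hepatitis B reactivation in subjects treated with ibrutinib. It notes that causality has not been established and asks for monitoring of signs and symptoms. The question can also return after enrolment. Protocol 8.4 allows study drug to be reintroduced in both cohorts, its list of reintroduction criteria has no hepatitis item, and the schedules in Appendices C, D and E show no hepatitis serology.

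**Working it through.** No sample size, power, alpha or event count is involved, so there is no figure to reproduce. The check is to apply each text to each kind of result. Below, PCR means the assay that matches the positive marker; 7.1.2.4 names hepatitis B DNA and hepatitis C RNA separately.

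| Screening result | Serology clause of criterion 11 (synopsis, 4.2) | 7.1.2.4 |
|---|---|---|
| HBsAg positive, PCR positive | Excluded | Excluded |
| HBsAg positive, PCR negative | Not excluded | Excluded |
| HBsAg negative, core or HCV antibody positive, PCR positive | Excluded | Excluded |
| HBsAg negative, core or HCV antibody positive, PCR negative | Not excluded | Not excluded |

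The texts part in the second row only.

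Next, can the sentences be reconciled?

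1. Criterion 11 makes a negative PCR a necessary condition. It does not say that a negative PCR is sufficient.
2. The last exclusion sentence in 7.1.2.4 adds a further condition. A site that excludes every HBsAg-positive subject breaks no sentence in any of the three places.
3. A site that enrols an HBsAg-positive, PCR-negative subject meets the serology clause of criterion 11 but breaks that sentence of 7.1.2.4.
4. Under the strict rule, naming HBsAg in the PCR sentence changes no eligibility decision, because the subject is excluded whatever the PCR shows. The wording is redundant in all three places, and its natural reading points the other way.

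Finally, does the strict rule appear elsewhere in the list that sites check? Section 4.2 has 22 numbered exclusion criteria. Criterion 11 is the only one that mentions HBsAg, and none of the 22 states a blanket HBsAg exclusion.

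**The case against.** The strongest reply is that nothing here contradicts. Criterion 11 sets a necessary condition, 7.1.2.4 adds another, and a careful site satisfies both by excluding the subject. This stands as logic. A reader might infer that criterion 11 expressly permits an HBsAg-positive, PCR-negative subject, or that the two sections cannot both be obeyed. The documents support neither reading. What remains is the implication: a PCR step set out for HBsAg-positive subjects, followed by an exclusion limited to PCR-positive ones, suggests that a negative result settles the matter.

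A second reply is that HBsAg positivity already counts as active infection under the opening sentence of criterion 11. An investigator could apply it that way. Criterion 13 offers another route, since it covers conditions that in the investigator's opinion "could compromise the subject's safety or put the study outcomes at undue risk". But criterion 11 does not define active infection by HBsAg, and its next sentence sends HBsAg-positive subjects to PCR. Exclusion by either route depends on the individual investigator.

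A third reply is that footnote k takes sites to 7.1.2.4, where the exclusion is explicit. That is so, and it makes an error less likely. It does not put the rule into Section 4.

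A fourth reply is that the correction comes late. SAP 1.1 says the Fixed Duration cohort was added after MRD enrolment was complete. Protocol 8.3.2 makes allowance for Fixed Duration subjects who had already passed Cycle 28 when Amendment 3 reached their site. No section says that Fixed Duration enrolment has closed, but the prospective effect of editing the entry rule is clearly small. Editing it would also leave the separate reintroduction criteria unchanged, which is why a check of existing serologies is worth adding.

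**Conclusion.** The point holds as a minor inconsistency in a safety eligibility rule. Section 4 omits an exclusion that 7.1.2.4 states, and criterion 11 implies the opposite in one situation: HBsAg positive with a negative PCR. The number of subjects is unknown and probably very small. The documents give no frequency, and I claim none. Endpoints, power and alpha are untouched.

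A reader might go further and infer that such a subject was enrolled, or would pass undetected into retreatment. The documents do not show this. Serology is a screening test, so a result should exist at the site. Protocol 8.4 requires Medical Monitor approval before reintroduction, sets limits on AST or ALT and on bilirubin, and excludes any condition that the investigator thinks could compromise safety. The gap is that nothing in 8.4 prompts anyone to look at the hepatitis B result.

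The conclusion rests on reading the three texts as current protocol wording; none of them is redacted or part of a change log. It also assumes that the strict rule is the intended one. That is the reading that breaks no sentence, but the sponsor should confirm it.

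**What to change.** State one rule in the same way in all three places:

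- In criterion 11, in the synopsis and in Section 4.2, add "Subjects who are HBsAg positive are excluded".
- In the synopsis, Section 4.2 and 7.1.2.4, remove HBsAg from the PCR sentence. Keep the PCR route for hepatitis B core antibody and hepatitis C antibody.
- Have the sponsor confirm that the strict rule was intended. If it was not, the sentence to change is the blanket exclusion in 7.1.2.4.

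Separately, ask sites to check existing screening serologies for any enrolled HBsAg-positive subject and to tell the Medical Monitor before any reintroduction under Protocol 8.4. The tests are run at local laboratories, and the documents do not say that results are entered centrally. The request should therefore go to sites and should not be assumed to be a database query.

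The cost is text edits in three places and one look-back at results already obtained. Protocol 12.14 requires ethics committee and site approval before an amendment takes effect, so the edit can wait for the next amendment. The serology check need not wait for it. The downside is that a few PCR-negative subjects whom criterion 11 alone would not exclude become ineligible.
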